12.2.4.2 Evaluation of Non-Target Lesions

Complete Response (CR):

Disappearance of all non-target lesions and normalization of tumor marker level. All lymph nodes must be non-pathological in size (<10 mm short axis)

Note: If tumor markers are initially above the upper normal limit, they must normalize for a patient to be considered in complete clinical response.

Non-CR/Non-PD:

Persistence of one or more non-target lesion(s) and/or maintenance of tumor marker level above the normal limits

Progressive Disease (PD):

Appearance of one or more new lesions and/or *unequivocal progression* of existing non-target lesions. *Unequivocal progression* should not normally trump target lesion status. It must be representative of overall disease status change, not a single lesion increase.

12.2.5 Overall Response Assessment

Table 1: For Patients with Measurable Disease (i.e., Target Disease)

Target Lesions	Non-Target Lesions	New Lesions	Overall Response	Best Overall Response when Confirmation is Required*
CR	CR	No	CR	≥ 28 days Confirmation
CR	Non-CR/Non-PD	No	PR	≥ 28 days Confirmation
CR	Not evaluated	No	PR	
PR	Non-CR/Non-PD/not evaluated	No	PR	
SD	Non-CR/Non-	No	SD	documented at least once ≥ 28 days from baseline

	PD/not evaluated			
PD	Any	Yes or No	PD	no prior SD, PR or CR
Any	PD**	Yes or No	PD	
Any	Any	Yes	PD	

* See RECIST 1.1 manuscript for further details on what is evidence of a new lesion.
 
** In exceptional circumstances, unequivocal progression in non-target lesions may be accepted as disease progression.
 
Note: Patients with a global deterioration of health status requiring discontinuation of treatment without objective evidence of disease progression at that time should be reported as “symptomatic deterioration.” Every effort should be made to document the objective progression even after discontinuation of treatment.
				

Table 2: For Patients with Non-Measurable Disease (i.e., Non-Target Disease)

Non-Target Lesions	New Lesions	Overall Response
CR	No	CR
Non-CR/non-PD	No	Non-CR/non-PD*
Not all evaluated	No	not evaluated
Unequivocal PD	Yes or No	PD
Any	Yes	PD

* ‘Non-CR/non-PD’ is preferred over ‘stable disease’ for non-target disease since SD is increasingly used as an endpoint for assessment of efficacy in some trials so to assign this category when no lesions can be measured is not advised
		

Table 3: Overall Response for Patients with Neuroblastoma and Measurable Disease

CT/MRI	MIBG	Bone Scan	Bone Marrow	Catechol	Overall
PD	Any	Any	Any	Any	PD
Any	PD	Any	Any	Any	PD
Any	Any	PD	Any	Any	PD
Any	Any	Any	PD	Any	PD
SD	CR/PR/SD	Non-PD	Non-PD	Any	SD
PR	CR/PR	Non-PD	Non-PD	Any	PR
CR/PR	PR	Non-PD	Non-PD	Any	PR
CR	CR	Non-PD	Non-PD	Elevated	PR
CR	CR	CR	CR	Normal	CR

12.2.6 Overall Best Response Assessment

Each patient will be classified according to his “best response” for the purposes of analysis of treatment effect. Best response is determined as outlined in [Section 12.8](#) from a sequence of overall response assessments.

12.3 Response Criteria for Patients with Solid Tumors and Evaluable Disease

12.3.1 Evaluable Disease

The presence of at least one lesion, with no lesion that can be accurately measured in at least one dimension. Such lesions may be evaluable by nuclear medicine techniques, immunocytochemistry techniques, tumor markers or other reliable measures.

12.3.2 Complete Response

Disappearance of all evaluable disease.

12.3.3 Partial response

Partial responses cannot be determined in patients with evaluable disease

12.3.4 Stable Disease (SD)

That which does not qualify as Complete Response (CR), Partial Response (PR), or Progressive Disease.

12.3.5 Progressive Disease

The appearance of one or more new lesions or evidence of laboratory, clinical, or radiographic progression.

12.3.6 Overall Best Response Assessment

Each patient will be classified according to his “best response” for the purposes of analysis of treatment effect. Best response is determined as outlined in [Section 12.8](#) from a sequence of overall response assessments.

12.4 Response Criteria for Neuroblastoma Patients with MIBG Positive Lesions

12.4.1 MIBG Positive Lesions

Patients who have a positive MIBG scan at the start of therapy will be evaluable for MIBG response. The use of ¹²³I for MIBG imaging is recommended for all scans. If the patient has only one MIBG positive lesion and that lesion was radiated, a biopsy must be done at least 28 days after radiation was completed and must show viable neuroblastoma.

12.4.2 The following criteria will be used to report MIBG response by the treating institution:

Complete response: Complete resolution of all MIBG positive lesions

Partial Response: Resolution of at least one MIBG positive lesion, with persistence of other MIBG positive lesions

Stable disease: No change in MIBG scan in number of positive lesions

Progressive disease: Development of new MIBG positive lesions

12.4.3 The response of MIBG lesions will be assessed on central review using the Curie

[figure not shown]
scale14 as outlined below. Central review responses will be used to assess efficacy for study endpoint. See [Section 8.2](#) for details on transferring images to the Imaging Research Center.

NOTE: This scoring should also be done by the treating institution for end of course response assessments.

The body is divided into 9 anatomic sectors for osteomedullary lesions, with a 10th general sector allocated for any extra-osseous lesion visible on MIBG scan. In each region, the lesions are scored as follows. The **absolute extension score** is graded as:

- 0 = no site per segment,
- 1 = 1 site per segment,
- 2 = more than one site per segment,
- 3 = massive involvement (>50% of the segment).

The **absolute score** is obtained by adding the score of all the segments. See diagram of sectors below:

The **relative score** is calculated by dividing the absolute score at each time point by the corresponding pre-treatment absolute score. The relative score of each patient is calculated at each response assessment compared to baseline and classified as below:

1. **Complete response:** all areas of uptake on MIBG scan completely resolved. If morphological evidence of tumor cells in bone marrow biopsy or aspiration is present at enrollment, no tumor cells can be detected by routine morphology on two subsequent bilateral bone marrow aspirates and biopsies done at least 21 days apart to be considered a **Complete Response**.
2. **Partial response:** Relative score ≤ 0.2 (lesions almost disappeared) to ≤ 0.5 (lesions strongly reduced).
3. **Stable disease:** Relative score > 0.5 (lesions weakly but significantly reduced) to 1.0 (lesions not reduced).
4. **Progressive disease:** New lesions on MIBG scan.

12.4.4 Overall Response Assessment

Table 5: Overall Response Evaluation for Neuroblastoma Patients and MIBG Positive Disease Only

If patients are enrolled without disease measurable by CT/MRI, any new or newly identified lesion by CT/MRI that occurs during therapy would be considered progressive disease.

MIBG	CT/MRI	Bone Scan	Bone Marrow	Catechol	Overall
PD	Any	Any	Any	Any	PD
Any	New Lesion	Any	Any	Any	PD
Any	Any	PD	Any	Any	PD
Any	Any	Any	PD	Any	PD
SD	No New Lesion	Non-PD	Non-PD	Any	SD
PR	No New Lesion	Non-PD	Non-PD	Any	PR
CR	No New Lesion	Non-PD	Non-PD	Elevated	PR
CR	No New Lesion	CR	CR	Normal	CR

12.4.5 Overall Best Response Assessment

Each patient will be classified according to his “best response” for the purposes of analysis of treatment effect. Best response is determined from the sequence of the overall response assessments as described in Table 3 in [Section 12.8](#).

12.5 Response Criteria for Neuroblastoma Patients with Bone Marrow Involvement

12.5.1 Bone Marrow Involvement

Bone marrow obtained within 28 days prior to study enrollment with tumor cells seen on routine morphology (not by immunohistochemical staining only) of bilateral aspirate or biopsy on one bone marrow sample.

Bone Marrow responses are determined by H&E Staining of bilateral bone marrow biopsies and aspirates.

Complete Response: No tumor cells detectable by routine morphology on 2 consecutive bilateral bone marrow aspirates and biopsies performed at least 21 days apart. Normalization of urinary catecholamines or other tumor markers if elevated at study enrollment.

Progressive Disease: In patients who enroll with neuroblastoma in bone marrow by morphology have progressive disease if there is a doubling in the amount of tumor in the marrow AND a minimum of 25% tumor in bone marrow by morphology. (For example, a patient entering with 5% tumor in marrow by morphology must increase to $\geq 25\%$ tumor to have progressive disease; a patient entering with 30% tumor must increase to $> 60\%$).

In patients who enroll without evidence of neuroblastoma in bone marrow will be defined as progressive disease if tumor is detected in 2 consecutive bone marrow biopsies or aspirations done at least 21 days apart.

Stable Disease: Persistence of tumor in bone marrow that does not meet the criteria for either complete response or progressive disease.

12.5.2 Overall Best Response Assessment

Each patient will be classified according to his “best response” for the purposes of analysis of treatment effect. Best response is determined from the sequence of the overall response assessments as described in [Section 12.8](#).

12.6 Response Criteria for Patients with CNS Tumors

12.6.1 Measurable Disease

Any lesion that is at minimum 10 mm in one dimension on standard MRI or CT, for CNS tumors.

12.6.2 Evaluable Disease

Evaluable disease is defined as at least one lesion, with no lesion that can be accurately measured in at least one dimension. Such lesions may be evaluable by nuclear medicine techniques, immunocytochemistry techniques, tumor markers, CSF cytology, or other reliable measures.

12.6.3 Selection of Target and Non-Target Lesions

For most CNS tumors, only one lesion/mass is present and therefore is considered a “target” for measurement/follow up to assess for tumor progression/response. If multiple measurable lesions are present, up to 5 should be selected as “target” lesions. Target lesions should be selected on the basis of size and suitability for accurate repeated measurements. All other lesions will be followed as non-target lesions. The lower size limit of the target lesion(s) should be at least twice the thickness of the slices showing the tumor to decrease the partial volume effect (e.g., 8 mm lesion for a 4 mm slice).

Any change in size of non-target lesions should be noted, though does not need to be measured.

12.6.4 Response Criteria for Target Lesions

Response criteria are assessed based on the product of the longest diameter and its longest perpendicular diameter. Development of new disease or progression in any established lesions is considered progressive disease, regardless of response in other lesions – e.g., when multiple lesions show opposite responses, the progressive disease takes precedence. Response Criteria for target lesions:

- **Complete Response (CR):** Disappearance of all target lesions.
- **Partial response (PR):** $\geq 50\%$ decrease in the sum of the products of the two perpendicular diameters of all target lesions (up to 5), taking as reference the initial baseline measurements.

- **Stable Disease (SD)**: Neither sufficient decrease in the sum of the products of the two perpendicular diameters of all target lesions to qualify for PR, nor sufficient increase in a single target lesion to qualify for PD.
- **Progressive Disease (PD)**: 25% or more increase in the sum of the products of the perpendicular diameters of the target lesions, taking as reference the smallest sum of the products observed since the start of treatment, or the appearance of one or more new lesions.

12.6.5 Response Criteria for Non-Target Lesions:

- **Complete Response (CR)**: Disappearance of all non-target lesions.
- **Incomplete Response/Stable Disease (IR/SD)**: The persistence of one or more non-target lesions.
- **Progressive Disease (PD)**: The appearance of one or more new lesions and/or unequivocal progression of existing non-target lesions.

12.6.6 Response criteria for tumor markers (if available):

Tumor markers will be classified simply as being at normal levels or at abnormally high levels.

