 - Autologous stem cell infusion including boost infusion: ≥ 42 days.
- h. Cellular Therapy: ≥ 42 days after the completion of any type of cellular therapy (e.g. modified T cells, NK cells, dendritic cells, etc.)
- i. XRT/External Beam Irradiation including Protons: ≥ 14 days after local XRT; ≥ 150 days after TBI, craniospinal XRT or if radiation to $\geq 50\%$ of the pelvis; ≥ 42 days if other substantial BM radiation.
- j. Radiopharmaceutical therapy (e.g., radiolabeled antibody, ^{131}I -MIBG): ≥ 42 days after systemically administered radiopharmaceutical therapy.
- k. Irinotecan, temozolomide and mTOR inhibitor exposure:
- i. Patients who have received prior single agent therapy with irinotecan, temozolomide, or an mTOR inhibitor, excluding ABI-009, are eligible.
 - ii. Patients who have received prior therapy with ABI-009 are not eligible.
 - iii. Patients who have previously received irinotecan and temozolomide in combination without progressive disease while on therapy are eligible.
 - iv. Patients who have previously received irinotecan and temozolomide in combination and had significant toxicity with these two drugs are not eligible.
 - v. Patients who have received prior therapy with all three agents in combination (i.e. irinotecan, temozolomide, and an mTOR inhibitor) are not eligible.

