4.2.2 Concomitant Medications

4.2.2.1 Corticosteroids:

Patients receiving corticosteroids must have been on a stable or decreasing dose of corticosteroid for at least 7 days prior to enrollment. If used to modify **immune adverse events** related to prior therapy, ≥ 14 days must have elapsed since last dose of corticosteroid (See [Section 4.1.7.1.d](#)).

4.2.2.2 Investigational Drugs:

Patients who are currently receiving another investigational drug are not eligible.

4.2.2.3 Anti-cancer Agents:

Patients who are currently receiving other anti-cancer agents are not eligible.

4.2.2.4 Anti-GVHD agents post-transplant:

Patients who are receiving cyclosporine, tacrolimus or other agents to prevent graft-versus-host disease post bone marrow transplant are not eligible for this trial.

4.2.2.5 Anticonvulsants: Patients must not have received enzyme-inducing anticonvulsants for at least 7 days prior to enrollment (see [Appendix X](#) for a list of enzyme-inducing and non enzyme-inducing anticonvulsants).

4.2.2.6 Anticoagulants: Patients who are currently receiving therapeutic anticoagulants (including aspirin, low molecular weight heparin, and others) are not eligible.

4.2.2.7 CYP3A4 or P-gp-active agents: Patients must not be receiving any **strong** CYP3A4 or P-gp inducers or inhibitors within 7 days prior to enrollment (see [Appendix XIV](#)). Moderate inducers or inhibitors of CYP3A4 and P-gp should also be avoided during ABI-009 treatment, if possible.

4.2.3 Study Specific:

a. Pulmonary Dysfunction:

- Patients with interstitial lung disease and/or pneumonitis are not eligible.

b. Allergic reactions:

- Patients with a history of allergic reactions attributed to compounds of similar composition, including macrolide and ketolide antibiotics, temsirolimus/other mTOR inhibitors, temozolomide or irinotecan are not eligible.
- Patients with hypersensitivity to albumin are not eligible.

c. Surgery:

- Patients who have had or are planning to have the following invasive procedures are not eligible:
 - Major surgical procedure, laparoscopic procedure, open biopsy or significant traumatic injury within 28 days prior to enrollment.
 - Subcutaneous port placement or central line placement is not considered major surgery. External central lines must be placed at least 3 days prior to enrollment and subcutaneous ports must be placed at least 7 days prior to enrollment.
 - Core biopsy within 7 days prior to enrollment.

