12.2.2 Disease Parameters

12.2.2.1 Measurable disease: Measurable lesions are defined as those that can be accurately measured in at least one dimension (longest diameter to be recorded) as ≥ 20 mm by chest x-ray, as ≥ 10 mm with CT scan, or ≥ 10 mm with calipers by clinical exam. All tumor measurements must be recorded in millimeters (or decimal fractions of centimeters).

Note: Tumor lesions that are situated in a previously irradiated area must show definitive evidence of progression to be considered evaluable.

12.2.2.2 Malignant lymph nodes: To be considered pathologically enlarged and measurable, a lymph node must be ≥ 15 mm in short axis when assessed by CT scan (CT scan slice thickness no greater than 5 mm). At baseline and in follow-up, only the short axis will be measured and followed.

12.2.2.3 Non-measurable disease: All other lesions (or sites of disease), including small lesions (longest diameter < 10 mm or pathological lymph nodes with ≥ 10 to < 15 mm short axis), are considered non-measurable disease. Bone lesions, leptomeningeal disease, ascites, pleural/pericardial effusions, lymphangitis cutis/pulmonitis, inflammatory breast disease, and abdominal masses (not followed by CT or MRI), are considered as non-measurable.

Note: Cystic lesions that meet the criteria for radiographically defined simple cysts should not be considered as malignant lesions (neither measurable nor non-measurable) since they are, by definition, simple cysts. 'Cystic lesions' thought to represent cystic metastases can be considered as measurable lesions, if they meet the definition of measurability described above. However, if non-cystic lesions are present in the same patient, these are preferred for selection as target lesions.

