12.6.7 Overall Response Assessment

The overall response assessment takes into account response in both target and non-target lesions, the appearance of new lesions and normalization of markers (where applicable), according to the criteria described in the table below. The overall response assessment is shown in the last column, and depends on the assessments of target, non-target, marker and new lesions in the preceding columns.

Target Lesions	Non-target Lesions	Markers	New Lesions	Overall Response
CR	CR	Normal	No	CR
CR	IR/SD	Normal	No	PR
CR	CR, IR/SD	Abnormal	No	PR
PR	CR, IR/SD	Any	No	PR
SD	CR, IR/SD	Any	No	SD
PD	Any	Any	Yes or No	PD
Any	PD	Any	Yes or No	PD
Any	Any	Any	Yes	PD

Each patient will be classified according to his “best response” for the purposes of analysis of treatment effect. Best response is determined as outlined in [Section 12.8](#) from a sequence of overall response assessments.

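### CNS complete and partial responses carry no corticosteroid condition, and it is unclear whether the irradiated-lesion condition covers CNS lesions

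*Combined protocol and SAP*

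**What the plan says.** Section 12.6.4 sets the measure for CNS target lesions: "Response criteria are assessed based on the product of the longest diameter and its longest perpendicular diameter". Partial response is a fall of at least 50% in the summed products from baseline. Progression is "25% or more increase in the sum of the products of the perpendicular diameters of the target lesions" from the smallest sum on treatment, or a new lesion. Section 12.6.7 then combines the findings: "The overall response assessment takes into account response in both target and non-target lesions, the appearance of new lesions and normalization of markers".

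Corticosteroids are addressed at entry. Section 4.2.2.1 says: "Patients receiving corticosteroids must have been on a stable or decreasing dose of corticosteroid for at least 7 days prior to enrollment". Section 4.1.7.1.d adds a washout when steroids were given for immune adverse events. In the visible text, steroid dose does not appear in Sections 12.6 or 12.7 or in the Section 8.1 evaluation table.

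On irradiated lesions, Section 12.2.2.1 (solid tumors) says: "Tumor lesions that are situated in a previously irradiated area must show definitive evidence of progression to be considered evaluable". The CNS definition of measurable disease in 12.6.1 is "Any lesion that is at minimum 10 mm in one dimension on standard MRI or CT, for CNS tumors", and neither it nor the target-lesion rules in 12.6.3 repeat that condition. Section 4.1.4 refers every patient to 12.2 and 12.3 for the definitions of measurable and evaluable disease and does not cite 12.6.

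**The concern.** The entry rule treats a recent steroid increase as something to exclude before a patient starts, but nothing carries that control forward to the scans on which CNS response is judged. If a child's steroid is started or raised after the baseline scan and the lesion then looks smaller, the criteria as written return a partial response. That result enters the only secondary aim as evidence of activity of ABI-009 with irinotecan and temozolomide. In a small phase 1 study a single such case is visible in the summary.

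The irradiation question is related but separate. Section 12.6.3 notes that most CNS tumors present as one mass. If that mass was irradiated shortly before entry, the reader needs to know whether it qualifies as a target lesion, and the protocol points in two directions.

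**Working it through.** No figure in the plan is disputed, so there is none to reproduce. The check sets the passages side by side and sizes the thresholds.

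**Steroids: can the rules screen out a steroid effect?**
- Target-lesion rule (12.6.4): size change, disappearance or a new lesion. No steroid term.
- Overall response (12.6.7): a target partial response with no new lesion and no non-target progression gives an overall partial response whatever the marker status. Markers therefore do not screen it out.
- Confirmation (8.1 footnote 5; 12.7.1): a further scan on the next consecutive cycle. A steroid effect that lasts while the higher dose continues would pass.
- Central review (8.2.1): covers complete and partial responses and long-term stable disease. No instruction to consider steroid dose.
- Entry rule (4.2.2.1): covers the 7 days before enrollment only. Therapy is to start within 5 days of enrollment (3.9), so that window opens at most 7 + 5 = 12 days before the start of therapy. The baseline scan may be up to 14 days before the start (4.0). The entry rule therefore does not fix the dose at the baseline scan either.

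**Width of the response categories**, assuming both diameters change by the same proportion:
- Partial response: 1 − √0.50 = 0.293, a 29.3% reduction in each diameter. A 20 × 20 mm lesion (400 mm²) must reach 200 mm², about 14.1 × 14.1 mm, or 5.9 mm less in each diameter.
- Progression: √1.25 − 1 = 0.118, an 11.8% increase in each diameter. The same lesion must reach 500 mm², about 22.4 × 22.4 mm, or 2.4 mm more in each diameter.

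These figures show how much change moves a patient between categories. They do not show how often steroids cause it.

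**Weight of one miscounted response**, using the Section 11.1.1 projections as illustrative denominators (evaluability there concerns toxicity, so the response denominators may differ):
- 12 evaluable patients under Amendment #4: 1/12 = 8.3 percentage points.
- 36 patients overall: 1/36 = 2.8 percentage points.

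**Irradiated lesions.** Section 4.1.7.1.i allows entry from "14 days after local XRT", and 150 days after craniospinal radiotherapy. If therapy starts on the day of enrollment, a baseline scan 14 days earlier could coincide with the end of local radiotherapy. The end-of-Cycle-1 scan would then fall 14 + 21 = 35 days after it, and the end-of-Cycle-2 scan 14 + 42 = 56 days after it. Whether such a lesion may be a target depends on the reading. Following 4.1.4 into 12.2.2.1, it must first have clearly progressed. Following 12.6.1, size alone suffices.

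**The case against.** The strongest objection is low consequence. Aim 1.2.1 is preliminary, Section 11.5 reports response descriptively, no test or decision rule uses it, and the MTD rests on dose-limiting toxicity in Cycles 1 and 2. Confirmation and central review also limit transient effects. All of this stands and bounds the point. It does not remove it, since neither safeguard is directed at steroid dose.

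Several stronger readings are tempting, and the documents do not support them.
- A reader might infer that no CNS response can be attributed to treatment, or that lesion size is the sole criterion. Confirmation, central review, non-target lesions, new lesions and, for complete response, markers all enter the assessment.
- A reader might infer that the irradiated-lesion condition is definitely missing for CNS tumors. Section 4.1.4 makes it arguable that the condition already applies at entry. What can be shown is ambiguity.
- A reader might want progression withheld when steroid dose has changed. Progression governs removal (10.1a) and entry to Cycle 3 and later (5.2; 8.1 footnote 12). After the end of Cycle 2, scheduled scans are two cycles apart. Deferring progression would be a treatment-continuation rule and is outside this point.
- A reader might conclude that steroid dose goes unrecorded, or that the blank section number in Appendix XIV footnote 2 marks a lost response rule. The case report forms are a separate packet that is not available here, and that footnote belongs to a CYP3A4 table.

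**Conclusion.** The point holds in limited form. As written, a CNS partial response can be scored and confirmed while the steroid dose is above baseline, and the protocol gives no means of separating such cases in the activity summary. This rests on one assumption that the documents do not quantify: that a steroid start or increase can reduce the apparent size of a CNS lesion enough to matter. The CNS share, steroid use and size of the effect are not given. The number of misclassified patients therefore runs from none up to the number of CNS responders and cannot be narrowed. The bias concerns a descriptive secondary aim and leaves dose finding untouched.

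On prior irradiation, the finding is that Sections 4.1.4 and 12.2.2.1 do not agree clearly with 12.6.1 and 12.6.3 and must be reconciled.

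**What to change.** - In 12.6.4 and 12.6.7, state that a CNS complete or partial response counts in the response analysis only if the corticosteroid dose at the response scan and at the confirmatory scan is no higher than at baseline. Define baseline as the dose at the baseline scan. List separately any patient who meets the size criterion on a higher dose.
- Record corticosteroid dose at baseline and at each disease evaluation, if the case report forms do not already do so.
- Report any CNS progression that coincides with a steroid change with a descriptive flag. Leave the definition of progression and the continuation rules as they are.
- Reconcile 4.1.4 and 12.2.2.1 with 12.6.1 and 12.6.3, stating whether the irradiated-lesion condition applies to CNS lesions.

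None of this affects who continues treatment. Section 5.2 asks for at least stable disease, so a response left out of the analysis does not change a patient's standing. The cost is a few sentences and one data field at existing evaluations, with no extra scans. The downside is that a few genuine CNS responses may not be counted because the steroid dose rose for another reason.
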